Termination. If a participant does not meet a single target goal following 3 sessions, the RST intervention will cease, and data will contribute to the intention-to-treat analysis as outlined in the research plan.

Non-participation. Each participant has the alternative to not participate in the study. If the participant chooses not to participate, it will not affect their current and/or future medical care or any benefits to which they are entitled.

Human Subjects Involvement and Characteristics

A total of 51 Veteran and non-Veteran volunteers will be recruited.

Inclusion of Women, Minorities and/or Children. *No participants will be excluded based on sex or race/ethnic origin*. Sex, ethnic, and racial information will be collected as part of the demographic information. Participants will be selected based on the inclusion criteria identified above.

Ethnicity (i.e., Hispanic/Latino, Non-Hispanic/Latino) will be recorded separately from race. All applicable racial categories (i.e., American Indian/Alaskan Native, Asian, Native Hawaiian or other Pacific Islander, Black/African American, White) will be recorded for each participant by study personnel. All ethnic and racial totals will be reported, including specific categories for those participants who report mixed racial descent (any combinations recorded by study personnel). No outreach program to recruit minorities is planned because all eligible individuals, regardless of race or ethnic origin, will be invited to participate. Historic data indicates men are twice as likely to have OP HNC compared to women.⁴ Recent studies from three countries (United States, United Kingdom, and Romania) suggest there is a 2:1 ratio of males to females diagnosed with HNC and make up 80% Caucasian, 11% Black/African American, 4% Hispanic, and 5% other racial/ethnic categories.¹²²⁻¹²⁴ It is anticipated that the sex, ethnic and racial mix of this study sample will roughly parallel these demographic data.

ANTICIPATED TARGETED/PLANNED ENROLLMENT: Number of Subjects			
Ethnic Category	Sex		
	Females	Males	Total
Hispanic or Latino	0	3	3
Not Hispanic or Latino	2	35	37
Ethnic Category: Total of All Subjects *	2	38	40
Racial Categories			
American Indian/Alaska Native	0	0	0
Asian	0	0	0
Native Hawaiian or Other Pacific Islander	0	0	0
Black or African American	0	6	6

White	2	32	34
Racial Categories: Total of All Subjects *	2	38	40

Children will not be eligible for enrollment in this project. Children do not commonly present with HNC. Further, respiratory-swallow phase patterns and training have not been systematically studied in dysphagic children. This supports their exclusion from this project that is based on preliminary data acquired in adults.

5.2 *Recruitment Methods*

A total of 51 Veteran and non-Veteran volunteers will be enrolled with the goal of 40 meeting inclusion criteria. Potential participant volunteers will be identified by the following methods of participant recruitment, all approved by the VA Institutional Review Board (IRB): 1) follow-up medical visits, particularly the otolaryngology-head and neck clinics; 2) announcement of the study in the VA patient bulletins and monitors (Appendix); 3) community-based outpatient clinics (CBOCs); and 4) review of patient medical charts (CPRS) at Hines VA to find patients that match the diagnosis of oropharyngeal cancer and dysphagia diagnoses (letters will be mailed to these potential patients with information in regards to the study. Also included will be a brief survey, along with a postage paid return envelope, which allows the patients to indicate if interested in participating or not); 5) posting of recruitment flyers at Jesse Brown VA, Loyola University Medical Center, Northwestern Memorial Hospital, University of Chicago Medical Center, and Northwestern Medicine Healthcare Partners.

Participants will be compensated for their participation in the study to assist support of their time and travel. Participants will receive \$40 for each MBSS and \$30 for each RST session. For participants randomized to immediately undergo the intervention, they have the potential maximum of earning \$440. The participants randomized to the control group will undergo one additional MBSS procedure immediately prior to their cross-over to the intervention arm, for a potential maximum of \$480. Participant payment will be made according to the current local fiscal office guidance and processes. Planned payments will be approved by appropriate study personnel for disbursement according to this schedule:

- Payment 1: after first study visit to determine eligibility for intervention (which includes first MBSS)
- Payment 2: after week 1 of intervention
- Payment 3: after week 2 of intervention
- Payment 4: after week 3 of intervention
- Payment 5: after week 4 (final) of intervention
- Payment 6: after post-intervention study procedures
- Payment 7: after 1-month follow-up study procedures
- Payment 8: after 3-months follow-up study procedures
- Payment 9: after 6-months follow-up study procedures
- One additional payment will be made to those participants assigned to the control arm. This payment will be dispersed immediately after the MBSS procedure immediately prior to starting RST treatment.

5.3 *Informed Consent Procedures*

Informed consent will be obtained by all trained study personnel, including PI, Study Coordinator and SLP, using a VA IRB approved informed consent form. All participants will be explained the study procedures, potential risks, and benefits by consenting personnel.

5.4 *Inclusion/Exclusion Criteria*

Inclusion and Exclusion Criteria. **Entry inclusion criteria:** 1) ≥ 21 years of age; 2) signed informed consent; 3) at least 6 months post head and neck cancer treatment for oral cancer, oropharyngeal cancer, laryngeal cancer, or hypopharyngeal cancer; 4) consumes ≤ 2 alcoholic drinks daily and 5) English speaking. **Entry exclusion criteria:** 1) known allergy or dietary restriction for materials used during the exam; 2) severe chronic obstructive pulmonary disease (COPD); and 3) recent history of aspiration pneumonia (past 12 months). **Intervention inclusion criteria:** 1) pass Montreal Cognitive Assessment (MoCA) (≥ 26)⁸⁷. **Intervention exclusion criteria:** 1) fails MoCA (< 26); and 2) inability to tolerate at least one liquid consistency (PAS ≥ 7). Women of child-bearing age will be screened via questionnaire in accordance with VA Medical Center policy precautions. Women who are pregnant will be excluded from this trial given that five MBSSs are required and the risk of any radiation to the fetus exceeds the potential benefit of this study. Men will also be counseled regarding the risks of radiation exposure to their reproductive organs. Hospital policy precautions for radiation safety will be applied. Informed consent will be obtained by the examining speech-language pathologist (SLP). The study procedures, potential risks, and benefits will be explained to all participants, and caregivers when appropriate, by the examining SLP. It will be explained that participation in the study will not have any impact on the quality of his/her present and/or future care as a patient. Further, if a participant chooses not to participate or drops out of the study at any time, there will be no consequences of this action. There will be no additional study sites involved with this research.

Cognitive Criteria. There exists the possibility that study volunteers may experience co-existing cognitive problems that preclude the learning of a new motor task. Participants will be screened immediately following consent (prior to the baseline modified barium swallow study, MBSS) for cognitive impairment using the MoCA⁸⁷ – a cognitive screening test designed to assist health professionals for detection of mild cognitive impairment. The standardized procedure covers the following cognitive domains: visuospatial/executive, naming, memory, attention, language, abstraction, delayed recall, and orientation. Scores for each domain are summed and a total score is obtained that can be adjusted for educational level. MoCA scores < 26 suggest cognitive impairment. Thus, participants with a total MoCA score of 25 or less will be excluded from further participation.

Pulmonary Criteria. There is some evidence indicating that pulmonary function status may impact respiratory-swallow phasing and swallowing impairment,¹¹⁶⁻¹¹⁹ and many patients with HNC present with varying degrees of disordered pulmonary function. An important covariate of upper airway function is lower airway disease. Since smoking is a risk factor for both HNC and COPD, a number of patients have both diagnoses. Although we did not find an association between pulmonary function and the ability to train in our preliminary study, it remains unclear whether expiratory airflow obstruction changes expiratory time constants and potentially impacts swallowing timing or physiology. Consequently, all participants will be screened for the presence of pulmonary disease if they meet the cognitive screening criteria prior to the baseline MBSS. Pulmonary screening will include spirometry performed by a licensed pulmonary function technician and reviewed for compliance with the American Thoracic Society standards.^{117,118} These data will permit further study of the impact of pulmonary function on respiratory-swallow

Clinical Impact of Respiratory-Swallow Training on Refractory Dysphagia in OP HNC Funding (1010498-19)

phasing and the outcome variables in the proposed trial. The best single objective measurement of COPD severity is the forced expiratory volume in 1 second (FEV1).^{120,121} FEV1 will be analyzed as a covariate in analyses. Patients with severe COPD (FEV1<50% predicted) will be excluded from further study and will not receive the baseline MBSS.

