5.0 Study Procedures

5.1 Study Design

Specific Aim 1 – Respiratory-Swallow Training (RST) In-Clinic.

Patient Sample. A total of 51 participants will be enrolled with the goal of 40 recruited if they meet inclusion criteria. Forty participants will be randomly assigned (1:1) to either RST (intervention arm) or no active treatment (control arm), which is considered standard of care in this patient population. Participants assigned to the control arm will cross-over after 4 weeks of no active treatment to undergo RST. All patients will participate in a pre-RST MBSS. The purpose of this pre-RST MBSS is to identify their baseline pre-RST respiratory-swallow phase patterning by specifying the respiratory phase and volume at time of swallowing initiation, assess swallowing physiology (MBSImP) and assess clinical swallowing status (FOIS). Participants will be included in the study if they are able to swallow at least one liquid consistency without visible tracheal residue (PAS ≤ 6) and without the use of a compensatory strategy or swallow maneuver. Participants will be excluded if they have known allergy or dietary restriction for contrast materials or liquids used during the MBSS or training, currently drinking greater than two drinks per day, severe COPD, are unable to swallow one liquid consistency without the use of a compensatory strategy or swallow maneuver without aspiration, or history of aspiration pneumonia within the past 12 months.

Clinician Examiners, Raters and Trainers. Expert speech-language pathologists (SLPs) will participate in this study to provide RST training, conduct the MBSSs, and perform blinded MBSImP and PAS scoring (i.e., without benefit of patient identifiers, randomization, clinical information, and performance during RST). The SLPs will not crossover study roles.

Spirometry. All Veteran and non-Veteran participants will undergo PFTs using spirometry performed by American Thoracic Society standards to stage COPD.⁸⁸ Participants will be characterized into Global Initiative for Obstructive Lung Disease (GOLD) spirometric groups on the basis of % predicted FEV1.⁹⁰ Any patient with severe stage COPD will be excluded from the study to protect against risk since experience in our clinic and previous study showed these patients could not consistently perform the proposed training tasks.

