Modified Barium Swallowing Study (MBSS). MBSSs will be conducted in a routine fluoroscopy suite with a radiologist and examining SLP present. Fluoroscopy will be captured using a high-resolution imaging platform (TIMS 2000 SP DICOM System, Foresight Imaging, Chelmsford, MA). Participants will be seated upright and positioned in the lateral and anterior-posterior viewing planes. The visualization field will include the lips anteriorly, nasal cavity superiorly, cervical spinal column posteriorly, and the pharyngoesophageal segment (PES) inferiorly.^{78,79,91-93} The MBSImP, a standardized, reliable, *reproducible*, and valid approach for the execution, assessment and interpretation of the MBSS, will be used to provide measures of swallowing physiology pre- and post-intervention. The MBSImP protocol includes 12 swallowing tasks via presentations of varying bolus consistencies, bolus volumes, and presentation methods. However, consistent with the MBSImP protocol, if a patient is unable to tolerate a swallow task because of safety (aspiration) concerns, that task is not included, and the component scores associated with the missing task are given the worst (highest) score in keeping with the statistical methods inherent in the tool. Standardized ready-to-use barium contrast (Varibar® E-Z-EM, 40% w/v, Bracco Inc.) will be presented. These swallowing tasks include: thin barium (two trials of 5ml via teaspoon, one cup sip, and sequential swallows from cup), nectar barium (one trial of 5ml via teaspoon, one cup sip, and sequential swallows from cup), thin-honey barium (one trial of 5ml via teaspoon), pudding barium (one trial of 5ml via teaspoon), a solid (one-half portion of a Lorna Doone shortbread cookie coated with 3ml pudding barium), and two additional tasks presented in the anterior-posterior viewing plane (one trial each of 5ml nectar and pudding barium). Participants will be asked to maintain a neutral

posture during the drinking tasks, since alteration of posture from the upright position may affect respiratory-swallow phasing.⁹³

Respiratory-Swallow Phase Pattern Measures.

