Respiratory Recording and Lung Volume Calibration. Respiratory movements of the rib cage (RC) and abdomen (AB) will be recorded using respiratory inductance plethysmography (RIP) (Inductotrace System; Ambulatory Monitoring, Inc., Ardsley, New York) coupled to a data acquisition system (BIPOAC Systems, Inc., Santa Barbara, CA, Model MP150).⁹⁵ The RC band will be placed around the rib cage at midsternal level, and the AB band will be placed around the abdomen below the lowest rib. The method developed by Banzett et al.⁹⁶ will be used to calibrate the summed RC and AB signals provided by the Inductotrace system to infer respiratory lung volume changes.⁹⁶ A standard ratio (RC to AB) of 2:1 will be used to weight the signals (originally recorded at equal gain) prior to being summed. The summed signal (in voltage) will then be calibrated using a known volume excursion to provide an estimate of lung volume. Each participant will be instructed to breathe in and out 3 times filling and emptying a Spirobag with a fixed 800 ml of air in the bag.

The optimal respiratory-swallow phase pattern targeted in RST is swallow initiation during the expiratory limb of the breathing cycle between mid-to-low quiet breathing lung volumes with resumption of expiration upon swallow completion. Respiratory data will be time synchronized with videofluoroscopic imaging data. Cycle detection and threshold algorithms programmed within AcqKnowledge software will be used to measure respiratory-swallow phase patterning for each subject during pre-intervention, post-intervention and follow-up.⁹⁵

Functional Swallowing Measures.

Functional Oral Intake Scale (FOIS). The FOIS, a 7-point ordinal scale shown to associate with dysphagia severity, will be completed by the examining SLP to rate functional oral intake.¹⁷ Level 1 implicates nothing by mouth, while a Level 7 indicates total oral diet without restrictions. Initial psychometric testing revealed high inter-rater reliability, validity, and sensitivity to change in oral intake status.¹⁷ A clinical meaningful improvement on the FOIS has been defined as an improvement of ≥ 2 levels.¹⁸

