MBSImP Scores. The MBSImP scores will provide a primary outcome measure of swallowing impairment. The MBSImP is a validated and reliable scoring system for the quantification of swallowing impairment from MBSS recordings.^{13,14,19} This tool has an ordinal scoring schema that permits quantification of oral, pharyngeal, and esophageal components of swallowing physiology. The operational definitions for the component scores represent a unique and unambiguous observation of structural movement and bolus flow. Seventeen physiologic components will be scored on a previously validated, rank order scale from least to most impaired. The scale for components ranges from 0-2 to 0-4 for each physiologic component.¹⁴ Years of field testing shows scores of 0 or 1 for the physiologic components of lip closure, oral residue, pharyngeal residue, and tongue base retraction are considered to be within normal limits.¹¹² For all other components, scores greater than 0 represent some level of impairment. Two methods will be used for MBSImP scoring: swallow-by-swallow (SS) and overall impression (OI). SS scoring assigns an MBSImP score for all applicable physiologic components for each of the 12 swallowing tasks given during the protocol. SS scores will be recorded for each participant. The highest (worst) score will be given during SS scoring when the participant's condition or performance on a previous swallowing task results in the withholding of a subsequent swallowing task for safety concerns.^{9,52} Additionally, missing data in SS interpretation will result if a participant refuses a swallowing task.⁵² As such, we will only include scores for swallowing tasks that are actually presented.

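### Masking is specified only for MBSImP and PAS scoring; the SLP who conducts the swallow study and assigns FOIS is not stated to be masked to arm

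*Combined protocol and SAP*

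**What the plan says.** Section 5.1, Clinician Examiners, Raters and Trainers, gives SLPs three jobs: training, conducting the modified barium swallow studies (MBSSs), and scoring. Masking is attached to the third, where SLPs will "perform blinded MBSImP and PAS scoring (i.e., without benefit of patient identifiers, randomization, clinical information, and performance during RST"). The paragraph adds: "The SLPs will not crossover study roles".

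For FOIS, the Functional Swallowing Measures text in 5.1 says the scale "will be completed by the examining SLP to rate functional oral intake". The next paragraph gives PAS to the scoring SLP instead. Section 5.6 judges clinical efficacy by comparing change in FOIS from visit 0 to visit 1 between arms. FOIS is the Aim 1 secondary outcome; MBSImP is primary.

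On the swallow study itself, 5.1 says "MBSSs will be conducted in a routine fluoroscopy suite with a radiologist and examining SLP present". If a task cannot be given because of aspiration concerns, "the component scores associated with the missing task are given the worst (highest) score". The MBSImP Scores paragraph (5.1, repeated in 5.6) applies the worst score when the participant's condition or an earlier task "results in the withholding of a subsequent swallowing task for safety concerns". It then turns to refused tasks and closes with "we will only include scores for swallowing tasks that are actually presented".

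**The concern.** Controls cross over to training after visit 1, so the change from visit 0 to visit 1 is the only randomised comparison. The comparator is no active treatment, a setting in which an assessor who knows the arm may expect improvement in one group. FOIS depends on an assessor's rating of intake. If the SLP making it knows who has just finished training, expectation can enter the rating, and neither masked video scoring nor the planned re-scoring touches it.

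Masked scoring also protects only what was filmed. If the worst score is imputed for a task that was not given, the rater has no image to judge. The decision not to give the task then becomes data, made by someone whom the plan does not describe as masked.

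**Working it through.** The plan gives no figure for this point, so there is none to reproduce. The check is mainly textual.

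**1. Who is masked.** Of the trainer, examiner and scorer roles in 5.1, only scoring carries a masking statement. No other section masks the examiner, and none says the examiner knows the arm. The accurate description is silence.

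**2. Whether role separation closes the gap.** It keeps the trainer from examining or scoring. It does not hide allocation from the examiner.

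**3. Whether arm could be learned.** Visit 1 is post-training in one arm and 4 weeks after baseline in the other (5.6). The control arm has an extra MBSS just before cross-over (5.2), so scheduling may reveal arm. Section 8.0 plans monthly meetings of all study personnel on progress and interpretation of outcomes, with no exception for examiners.

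**4. Whether FOIS has another safeguard.** The 20% re-scoring for rater reliability covers MBSImP and PAS. No second FOIS rating is described.

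**5. Whether withholding reaches MBSImP.** The worst-score rule says yes. The presented-tasks sentence says no if it governs all missing tasks; it follows the sentence on refusals and may cover only those. The MBSImP Scores paragraph also describes two scoring methods, swallow-by-swallow and overall impression, and states the worst-score rule for the first. The primary analysis in 5.6 does not say which method it uses. This route is therefore open but unsettled.

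**6. Illustration for FOIS.** Only the 20 per arm comes from the plan (5.1). Assumed: no true effect, two-sided 0.05, a normal approximation, and one in five trained participants rated one level too high, a mean shift b = 0.2. The documents give no SD for change in FOIS, so 0.75, 1.0 and 1.5 are tried.

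- SE = SD × √(2/20); rejection probability = Φ(b/SE − 1.96) + Φ(−b/SE − 1.96).
- SD 0.75: SE 0.237, b/SE 0.843, probability 13.5%.
- SD 1.0: SE 0.316, b/SE 0.632, probability 9.7%.
- SD 1.5: SE 0.474, b/SE 0.422, probability 7.1%.

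**7. Illustration for MBSImP.** Assumed: the worst-score rule applies, the 12 tasks have equal weight, the component is dichotomised, and each control participant has one extra task withheld. The shift in the swallow-level impaired rate is (100/12) × s points, where s is the share of those tasks that would have scored unimpaired.

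- s = 1 − 0.782 = 0.218 (pilot pre-training rate for laryngeal vestibular closure, Table 3): 1.8 points.
- s = 1 − 0.555 = 0.445 (pilot post-training rate): 3.7 points.
- s = 1 (upper limit): 8.3 points.

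For scale, the pilot change in that component was 78.2 − 55.5 = 22.7 points. The plan states neither equal weighting nor a withholding rate.

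**The case against.** A reader might infer that the examining SLP is unmasked, decides which tasks to withhold, and so biases the primary endpoint towards training. The documents do not support that. They are silent on the examiner's masking. They name no one as deciding on withholding, and a radiologist is also in the suite. The stated trigger is the participant's condition or an observed earlier task. The presented-tasks sentence may remove the imputation altogether. The direction and size of any effect are likewise not established.

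There is more to be said for the plan. Scorer masking is broad, covering identifiers, randomisation, clinical information and training performance. Role separation removes the person most invested in the training result from both examining and scoring. FOIS is secondary, and 5.1 cites high inter-rater reliability for it. The illustrative 0.2-level shift is one-tenth of the 2-level change that 5.1 calls clinically meaningful. If intake information comes from participants, who know their arm, masking the SLP leaves reporting bias in place.

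Most of this stands and limits the claim. It does not remove the FOIS gap. Agreement between raters does not protect against a shared expectation, and a shift well below clinical importance can still affect a significance test. Role separation is not concealment. Reporting bias is a reason to acknowledge a residual limit, not to leave a second source of bias open.

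**Conclusion.** The point holds for FOIS on the text alone: a clinician-rated outcome, compared between arms against no treatment, is assigned by an SLP for whom no masking is stated. It holds only conditionally for MBSImP. That route requires the worst-score rule to govern the analysed score and the person deciding on withholding to know the arm; the documents settle neither. It would overstate the case to say the primary endpoint is biased.

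The size of any bias cannot be determined. The FOIS range of 7.1% to 13.5% and the MBSImP range of 1.8 to 8.3 points rest on the assumptions listed and show only that modest distortions are not negligible with 20 per arm. This should be corrected because the remedy is cheap. It is not a reason to doubt the masked scoring of tasks that were presented.

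**What to change.** - **5.1, Clinician Examiners, Raters and Trainers:** extend masking at visits 0 and 1 to the examining SLP. That SLP should have no access to allocation, training records, arm-revealing scheduling or meeting discussion, and participants should be asked not to disclose their arm.
- **5.1, FOIS:** have the masked examining SLP assign FOIS from a standard intake form completed after the MBSS. An interview beforehand would invite disclosure just before any withholding decision.
- **Withheld tasks:** leave safety decisions unchanged. State who makes them, log each withheld task with its reason, and report the counts by arm.
- **MBSImP Scores (5.1 and 5.6):** reconcile the worst-score rule with the presented-tasks sentence, and state whether swallow-by-swallow or overall-impression scores feed the primary analysis.
- **5.6:** add a sensitivity analysis of MBSImP restricted to tasks presented at both visits.

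The cost is protocol wording, one case report form field for withheld tasks, a standard intake form and one extra analysis. No additional staff are needed, because examiners already hold a separate role.

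Masking will be imperfect. Participants know their arm, and their reported intake stays unmasked. Visit timing may also reveal arm: besides the pre-cross-over MBSS, 5.1 (Analysis Populations) refers to endpoint evaluation at 6 weeks while 5.6 sets the control visit at 4 weeks. Those two statements should be reconciled before relying on similar timing across arms.
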